20.3.2 Secondary Objectives

20.3.2.1 *To characterize the changes tumor EGFR, pEGFR, downstream signaling following a loading dose of cetuximab.*

Markers to be analyzed include, but are not limited to, EGFR and pEGFR. Some are measured on a continuous scale, and some on an ordinal scale. Continuous scale variables will be expressed as percent change from baseline, and the distribution will be characterized graphically (e.g., boxplot) and by descriptive statistics. After possible transformation (e.g., logarithmic), a single sample t-test will be used to evaluate the null hypothesis that the mean change equals 0. The percent change will be related to tumor control, progression-free survival, and the various assessments of toxicity by linear regression, logistic regression, or proportion hazards (Cox) regression, as appropriate. Ordinal scale variables will be expressed as difference from baseline, followed by a similar analysis plan to relate the differences to clinical outcomes. Because this is a secondary objective, all of the analyses will be guided by descriptive displays of the data.

20.3.2.2 *Compare normal mucosa EGFR to EGFR in the tumor sample.*

Repeated measures linear models will be used to characterize the change in differences between normal mucosa and tumor EGFR across the loading dose of cetuximab and determine if there are significant demographic or clinical variables that affect that change.

20.3.2.3 *To explore if baseline EGFR, BclxL, p.53 and p16 tumor expression are related to treatment response.*

The distributions of these markers in all patients, and in patients who do and do not respond, will be characterized by descriptive statistics (e.g., mean, median) and graphics (for example, boxplots). Because the number of treatment failures is likely to be small, these analyses will be considered strictly exploratory.

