7.5.2 Research Biopsies

Two research biopsies will be obtained. These research biopsies will be delivered directly to the Radiation Oncology research laboratory. The pre-treatment research biopsy (5-10 mm³) will be taken prior to therapy to assess baseline EGFR pathway activation. This pre-treatment biopsy will be performed for research purposes if a suitable clinical biopsy specimen is not available. A clinical specimen will be suitable if the biopsy was performed at UMHS within 30 days of consent. The second biopsy will be obtained 7 days (+/- 2 days) after the loading dose of cetuximab and will be examined for changes in EGFR pathway activation. Both biopsies will be performed in the clinic, under local anesthesia, by an otolaryngologist or oral surgeon who is a co-investigator of the study. The second biopsy will only be obtained if it can be done without general anesthesia.

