One high-density TMA will be constructed using a manual tissue arrayer (Beecher Instruments, [name], USA) at the core facility at the University of Michigan using standard methods. Tissue cores from the regions of interest (tumor tissues, before and after treatment) will be targeted for transfer to the recipient array block. At least three 0.6 mm diameter replicate tissue cores will be sampled from each subregion of the selected sample. The final TMA will consist of approximately 160 cores. After construction, 4 gm sections will be cut, and hematoxylin and eosin staining will be performed on the initial slide to verify the histology. Serial 4 gm sections will be further cut and transferred to positively charged slides, these sections will be subjected to standard immunohistochemical staining procedures. [name] lab have validated both total and phospho-antibodies that can be used successfully on formalin fixed tissue (26). The stained test slides will be reviewed by the head-and-neck pathologist co-investigator ([name]) for the expected pattern and appropriate intensity. The information about expected and appropriate staining for each antibody will be discussed with the other investigators to confirm the scoring criteria. The TMAs will be then stained by the staff at the Tissue Core. Each tissue core will be scored by a board certified oral and maxillofacial pathologist who is blinded as to the identity of the cores. Each tissue core will be scored for intensity of SCC cells staining: 1, undetectable; 2, weak; 3, moderate; 4, strong. Multiple TMA core measurements from the same subject will be averaged. This average score in its continuous scale will be used in all analyses.

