20.0 STATISTICAL CONSIDERATIONS

20.1 Study Design

This is a Phase II trial of seven weeks RT+cetuximab for head and neck cancer in patients with good prognoses to determine if this treatment will be at least as effective as, but less toxic than, standard therapy. A total of 43 patients will be enrolled in order to obtain 36 patients that complete radiation treatment and have both biopsies taken. Thus, both the clinical primary endpoints and scientific secondary endpoints can be analyzed, as EGFR tumor information is useful for determining potential mechanisms of resistance to cetuximab. Based on the experience of UMCC 9921 and UMCC 2-21, accrual is expected to average one patient per month. To be considered evaluable, a patient must complete the full course of radiation/cetuximab. If radiation and/or cetuximab was stopped or modified due to toxicity, the patient is still evaluable. Inevaluable patients will be replaced.

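### Section 20.3.2.1 leaves the scale of EGFR change open: percent change by default, with an optional log whose variable is not named; log(post/pre) for immunoblots and a simple difference for TMA scores would be better

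*Combined protocol and SAP*

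**What the plan says.** Section 20.3.2.1 defines one change variable for continuous markers: "Continuous scale variables will be expressed as percent change from baseline". It then tests it: "After possible transformation (e.g., logarithmic), a single sample t-test will be used", with the null hypothesis that the mean change is zero. The same variable goes into the outcome models: "The percent change will be related to tumor control, progression-free survival, and the various assessments of toxicity". No log ratio, log of raw values, offset or rule for when to transform is given. Ordinal markers are handled separately, as differences from baseline. The section closes with a qualifier: "Because this is a secondary objective, all of the analyses will be guided by descriptive displays of the data".

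Two kinds of measurement fall under the continuous rule. Section 15.3.1 yields scanned immunoblot band intensities, a positive scale. Section 15.3.2 scores each TMA core from 1 (undetectable) to 4 (strong), averages the cores per subject, and says: "This average score in its continuous scale will be used in all analyses".

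Section 20.1 gives the intended number of pairs: "A total of 43 patients will be enrolled in order to obtain 36 patients that complete radiation treatment and have both biopsies taken". Section 7.5.2 makes the second biopsy conditional: "The second biopsy will only be obtained if it can be done without general anesthesia". Section 2.0 expects downstream inhibition after the loading dose in most patients.

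**The concern.** Three features of the wording combine badly.

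- Percent change is bounded below at -100% and unbounded above, so a few large rises outweigh many falls in the mean.
- The remedy that the plan names, a logarithm, is optional and has no stated argument. Applied to percent change itself, it does not exist for values of zero or below, and falls are what Section 2.0 expects for the inhibited markers.
- On the 1-4 TMA score, the same one-step shift gives different percentages depending on where the patient started.

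At stake is the interpretation of the paired biopsies. The number with both biopsies helped set enrolment, and the second biopsy is taken to measure this change. A modest fall could be missed, or a marker with no typical change could be reported as rising. In the regressions, a fourfold rise enters as +300 and a fourfold fall as -75, so patients with large rises have undue leverage.

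**Working it through.** The documents give no power, SD or effect size for this test, so there is no planned figure to reproduce.

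**Inputs.** n = 36 pairs (Section 20.1). One-sample t-test of zero mean change (Section 20.3.2.1). Assumed: ln(post/pre) is normal with mean μ and SD s, with s from 0.3 to 0.8; two-sided alpha 0.05. Section 20.3.2.1 states no alpha; the primary analyses use 0.20.

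**Asymmetry.** One doubling and one halving: (100 - 50)/2 = +25%. On the log scale: (ln 2 + ln 0.5)/2 = 0.

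**Log of percent change.** The share of patients with a value of zero or below is Φ(-μ/s). With no median change this is 50%. With a 30% median fall and s = 0.5 it is Φ(0.357/0.5) = Φ(0.713) = 76%. Those patients would have no computable value under that reading.

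**Mean percent change.** This is 100 × (exp(μ + s²/2) - 1). With μ = 0 it is +4.6 at s = 0.3, +13.3 at s = 0.5 and +37.7 at s = 0.8. With a 20% median fall and s = 0.5 it is 100 × (0.8 × 1.133 - 1) = -9.3.

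**Simulation with no transformation (40,000 trials per setting, n = 36).** Probability of a significant increase when the median change is zero:

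| s | Percent change, alpha 0.05 | Log ratio, alpha 0.05 | Percent change, alpha 0.20 |
|---|---|---|---|
| 0.3 | 0.10 | 0.025 | 0.31 |
| 0.5 | 0.20 | 0.025 | 0.51 |
| 0.8 | 0.37 | 0.025 | 0.75 |

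The nominal upper tail is 0.025 at alpha 0.05 and 0.10 at alpha 0.20.

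Probability of detecting a real median fall, alpha 0.05:

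| Median fall | s | Percent change | Log ratio |
|---|---|---|---|
| 20% | 0.5 | 0.27 to 0.28 (separate runs) | 0.74 |
| 30% | 0.3 | 1.00 | 1.00 |
| 30% | 0.5 | 0.78 | 0.99 |
| 30% | 0.8 | 0.12 | 0.74 |
| 50% | 0.5 | 1.00 | 1.00 |

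With 20 pairs (an assumption, since the second biopsy is conditional) the pattern is the same but weaker: a significant increase in 0.09 of trials at s = 0.5 with no median change, and 0.21 against 0.47 for a 20% fall.

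**TMA score.** Moving from 1 to 2 is +100%; from 3 to 4 it is +33%. Complete loss of staining is -75% from a score of 4 and -50% from a score of 2. The difference (post minus pre) gives +1 for both one-step rises. The score ratio is bounded between 0.25 and 4, so the log-normal figures above apply to immunoblots and not to this score.

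**The case against.** The strongest reply is that the sentence need not mean a log of percent change. With a null of zero mean change, a sensible analyst would take log post minus log pre, which is the remedy proposed here. That stands: the text can be read so, and a reader who infers that the planned transformation must fail goes further than the wording supports. What remains is that the variable is not named and the transformation is optional.

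Second, the plan looks at distributions before testing. With no median change, a Shapiro-Wilk test rejects normality of raw percent change in about 43%, 80% and 99% of trials at s = 0.3, 0.5 and 0.8. If the analyst switches to the log ratio whenever that test has p < 0.05, significant increases fall to about 3 to 8%, and power for the 20% fall at s = 0.5 recovers to about 68%. This also stands, so the table describes an analysis left untransformed. The choice would still be made after seeing the data, with no stated rule.

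Third, a reader might infer that the percent-change test is invalid. It is not, for its own null. In the no-median-change settings, the arithmetic mean of percent change really is above zero. When that mean is truly zero, the percent-change test rejects in about 5%, 6% and 9% of trials at s = 0.3, 0.5 and 0.8, while the log-ratio test rejects in about 14%, 31% and 64%. The two tests target different quantities. The case for the log ratio is that the typical proportional change is the more natural target for band intensities.

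Fourth, a reader might infer that most of the power is lost in general. The two weakest percent-change rows (20% fall at s = 0.5, 30% at s = 0.8) each imply that only 67% of patients show any fall: Φ(0.223/0.5) and Φ(0.357/0.8) are both Φ(0.446). If 85% or 90% show a fall, one assumed reading of the expectation in Section 2.0, percent-change power is 99% or 100% at s = 0.5 and 92% or 99% at s = 0.8.

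**Conclusion.** The point holds as a defect of specification with a better choice readily available. The plan makes percent change the default for continuous markers, leaves the transformation optional and its argument unstated, and carries percent change into the outcome regressions. Left untransformed, immunoblot markers with no median change would show a significant increase in about 10% to 37% of trials against 2.5% nominal, and power for a modest fall can drop from 74% to about 27%. These sizes rest on a log-normal ratio, an assumed SD of 0.3 to 0.8, an assumed two-sided 5% level and 36 pairs, with the median or geometric mean ratio as the target. They shrink when most patients show a fall or when skew prompts a transformation. For the TMA score the objection is to the arbitrary dependence on baseline, without a quantified error rate. Severity is lower: the objective is secondary and guided by descriptive displays, and neither the primary analyses nor the stopping rule depends on it.

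**What to change.** In Section 20.3.2.1:

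- For immunoblot markers, prespecify log(post/pre) as the change variable, apply the one-sample t-test to it, and report the geometric mean ratio with a confidence interval. State a floor for undetectable values.
- For averaged TMA scores, use the simple difference (post minus pre), as the plan already does for ordinal variables.
- Use these same quantities as predictors in the outcome regressions.
- State the significance level for the test.

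Percent change can remain as a descriptive display. The cost is a few sentences of wording, with no extra patients, samples or assays. The floor is not an added burden peculiar to the log ratio, since percent change also breaks down when the baseline value is undetectable. Label: free improvement.

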20.4 Justification of Design

20.4.1 Early stopping rule for tumor control

The operating characteristics of the stopping rule were analyzed using the simulation tool in multc98. The probability the trial will be stopped early, and the distribution of the expected sample sizes, was calculated under the

assumption that the true probability of failure varied from 0.06 to 0.6. The operating characteristics are displayed in Table 2. For instance, if the true probability of failure equaled 0.2, 0.59 of the trials stopped early, 50% of the trials stopped after accruing 20 or fewer patients, and 25% of the trials stopped after accruing five or fewer patients.

True P(Failure)	P(Stop Early)	Sample Size Percentiles				
		10	25	50	75	90
0.06	0.05	35	35	35	35	35
0.2	0.59	5	5	20	35	35
0.3	0.91	5	5	10	15	30
0.4	0.99	5	5	5	10	15
0.5	0.99	5	5	5	5	19

Table 2 Operating characteristics of stopping rule for treatment failure

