8.0 RADIOTHERAPY

- 8.1 Immobilization, imaging and target definitions
 - 8.1.1 The technical details of RT planning will correspond to standard of care at the Department of Radiation Oncology as previously published (29).
 - 8.1.2 Target doses will be similar to the doses delivered in standard practice: 70 Gy at 2.0 Gy/fraction to primary tumor and to lymph nodes with clinical/radiological evidence of metastases, and 56-63 Gy at 1.6-1.8 Gy/fraction to subclinical disease around the primary tumor or to the surgical tumor excision bed, and to the lymph nodes at risk of metastasis, all in 35 fractions, over 7 weeks.
- 8.2 Optimization goals regarding the salivary glands will be:
 - 8.2.1 Mean dose to the parotid glands <26 Gy (at least one gland).
 - 8.2.2 The dose to the volumes of the submandibular glands and oral cavity outside the targets will be minimized.
 - 8.2.3 The doses to the swallowing structures (pharyngeal constrictors, glottic and supraglottic larynx) outside the targets will be minimized, aiming at mean dose < 50 Gy.
- 8.3 OPTIMIZATION CONSTRAINTS WILL BE:
 - 8.3.1 The maximal target PTV dose will be 110% of the prescribed dose.
 - 8.3.2 The minimum target PTV doses will be > 99% of the prescribed dose.
 - 8.3.3 The maximal dose outside the targets will be <105% of the prescribed dose delivered to at least 0.5 cc. volume.
 - 8.3.4 The maximal dose to the spinal cord, expanded 0.5 cm, will be < 50 Gy, to the non-expanded cord < 45 Gy, to the optic pathways < 50 Gy and to the brainstem <54 Gy.

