11.0 STUDY CALENDAR

Assessment	Pre-Treatment*	Day 0 Loading Dose	Day 7 (+/- 2 days)	Weekly during Treatment†	12-14 wks post RT (+/- 1 month)	Follow Up ³
H&P/Physician Evaluation	X			X	X	X
Smoking status and tumor HPV or p16 determination	X					
Biopsy	X		X ¹			
Buccal swab	X		X ¹			
COMP, Mg	X			X	X	
CBCP with diff	X			X	X	
PET-CT	X				X ²	
Dental Evaluation	X					
Toxicity Evaluation	X			X	X	X
QOL Questionnaire	X				X	X
Videofluoroscopy	X				X	X
Cetuximab		X		X		

* The pre-treatment period is prior to the administration of the cetuximab loading dose

† Radiation therapy will start within 4 days following Day 7 biopsy

¹Research biopsy will be performed 7 days (+/- 2 days) after cetuximab. This second biopsy will only be obtained if it can be done without general anesthesia.

²Restaging PET-CT will be obtained at 12-14 weeks.

³Follow Up: Examinations will be performed as comparable to clinical practice: at 1 month after the completion of therapy and then every 2 months during years 1 and 2, and at 3-month intervals during year 3. Toxicity evaluation will be collected at each visit. Quality of Life Questionnaires will be given to patients at follow-up visits 1, 3, 6, 12, 18, 24 and 36 months. Videofluoroscopy will be performed at 3, 12, and 24 months after therapy. Allowable windows for all these time points are +/- 1 month.

Note: Once patients discontinue treatment (Section 13.0) or have tumor progression/recurrence, they will be followed as clinically indicated for 3 years following the completion of radiation and/or cetuximab.

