20.2 Early Stopping Rules for Toxicity or Lack of Efficacy

In UMCC 9921 and UMCC 2-21, 2/32=6% of patients similar to those who will be treated in the current trial did not achieve tumor control. An early stopping rule will only be feasible for the identification of probability of treatment failure much higher than that. Table 1 describes the stopping rule for failure to control, which was derived using the method due to Thall, Simon and Estey [31], implemented in M.D. Anderson program multc98. **Failure is defined as local-regional recurrence or metastasis, but not second primary cancer, nor microscopic disease found in elective neck dissection, nor PET findings without correlative clinical evidence of disease persistence or recurrence.** For each number of patients enrolled, if *at least* as many failures as stated occurs (e.g., 2/5), accrual will be stopped. The rule was constructed to stop the trial if the probability that the failure rate of the experimental therapy exceeded 0.1625 (0.1 more than the historical rate) is at least 0.75.

# Patients	# Failures
5	2
10	3
15	4
20	5
25	6
30	7

Table 1 Stopping rule for failure to control tumor

Because the trial will only be stopped early for failure, and the stopping rule does not constitute an interim analysis, there will be no adjustment to the p-values of the analyses in Section 20.4.

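### Table 2's early-stopping figures assume every outcome is known at enrolment; at the planned accrual and follow-up, the stated 25% chance of stopping by five patients cannot be reached

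*Combined protocol and SAP*

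**What the plan says.** Section 20.2 gives the rule in Table 1: stop at 2 failures in 5 patients, 3 in 10, 4 in 15, 5 in 20, 6 in 25 or 7 in 30. The rule is indexed by enrolment ("For each number of patients enrolled") and acts when at least "as many failures as stated occurs (e.g., 2/5), accrual will be stopped". A failure is a local-regional recurrence or metastasis. The section sets no minimum follow-up, no time window and no accrual pause.

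Section 20.4.1 reports operating characteristics from the multc98 simulation tool: "if the true probability of failure equaled 0.2, 0.59 of the trials stopped early", and "50% of the trials stopped after accruing 20 or fewer patients, and 25% of the trials stopped after accruing five or fewer patients". It states no accrual rate and no delay before an outcome is known. Table 2 caps enrolment at 35.

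The timing is given elsewhere:
- Section 20.1: "accrual is expected to average one patient per month", and "A total of 43 patients will be enrolled in order to obtain 36 patients that complete radiation treatment and have both biopsies taken".
- Section 11.0: "Radiation therapy will start within 4 days following Day 7 biopsy".
- Section 8.1.2: the radiation doses are given "all in 35 fractions, over 7 weeks".
- Sections 9.1 and 9.3: first post-treatment exam at 1 month and restaging PET-CT at 12-14 weeks, each with a window of one month either way.

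**The concern.** A rule indexed by patients enrolled can act at row n only on failures already seen. Patients here enrol faster than they finish treatment and reach a first assessment, so the early rows fill with patients whose outcome is unknown. If Table 2 ignores this, it overstates how early the rule can act.

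Section 2.0 relies on strict stopping rules to protect good-prognosis patients who receive reduced-intensity treatment. Table 2 and its example sentence are the only statement of how soon that protection takes effect. A reader would expect a regimen with a 20% failure rate to be stopped by five patients in a quarter of trials and by 20 in half of them.

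**Working it through.** **Step 1: reproduce Table 2 with no delay.** Take cohorts of five, the Table 1 boundaries b(n) and all outcomes known at each look. Let f(n,k) be the probability of still being open after n patients with k failures. Then f(n,k) = sum over j of f(n-5, k-j) × Binomial(j; 5, p) for k < b(n); the mass at k ≥ b(n) stops at n.

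| True rate | P(stop), computed | P(stop), Table 2 |
|---|---|---|
| 0.06 | 0.046 | 0.05 |
| 0.20 | 0.594 | 0.59 |
| 0.30 | 0.912 | 0.91 |
| 0.40 | 0.992 | 0.99 |

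At 0.20, cumulative stopping is 0.263 by five patients and 0.521 by 20, which is the example sentence. All percentiles match except one cell (the 90th at 0.5: 10 computed, 19 stated). The plan does not state the zero-delay assumption; it is inferred from this match.

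**Step 2: who can count at the first row.** Seven days to the second biopsy, up to 4 days to radiotherapy and 49 days of radiotherapy make about 60 days, or 2 months. If patient i enrols at month i, radiotherapy ends at i+2, the 1-month exam is at i+3, and a failure seen 3 months after radiotherapy is known at i+5.

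Stopping with five enrolled requires two known failures before patient 6 enrols at month 6. With m assessable patients, P(at least 2) = 1 − (1−p)^m − m·p·(1−p)^(m−1). At p = 0.20:

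| Failures visible at | Assessable patients | P(at least 2) |
|---|---|---|
| Enrolment (Table 2) | 5 | 1 − 0.3277 − 0.4096 = 0.263 |
| End of radiotherapy | at most 4 (i+2 ≤ 6) | 1 − 0.4096 − 0.4096 = 0.181 |
| 1-month exam, up to patient 6 enrolling | 3 (i+3 ≤ 6) | 1 − 0.512 − 0.384 = 0.104 |
| 1-month exam, as patient 5 enrols | 2 (i+3 ≤ 5) | 0.2² = 0.040 |
| 3 months after radiotherapy | 1 (i+5 ≤ 6) | 0 |

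Restaging at the earliest edge of its window, about 8 weeks, also leaves two patients and 0.04. With random (Poisson) accrual averaging one a month, the figure is 0.07 for 1-month detection and 0.02 for 3-month detection.

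**Step 3: the rest of the table, under assumed timings.** Simulation with one patient a month, 2 months of treatment, a maximum of 35 and no inevaluable patients. A failure among the first n patients counts against row n whenever it is seen during accrual. Entries are the 10/25/50/75/90 percentiles of enrolment.

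| Case | 0.20 | 0.30 | 0.40 |
|---|---|---|---|
| Table 2 | 5/5/20/35/35 | 5/5/10/15/30 | 5/5/5/10/15 |
| 1-month exam, patient enrolling on stopping day not counted | 5/7/22/35/35 | 5/6/9/17/31 | 5/5/6/10/16 |
| 1-month exam, that patient counted | 6/8/23/35/35 | 6/7/10/18/32 | 5/6/7/11/17 |
| 3 months after radiotherapy, counted | 8/10/24/35/35 | 8/9/12/20/34 | 7/8/9/13/19 |
| Uniform over 24 months, counted | 17/24/35/35/35 | 13/18/24/32/35 | 11/15/20/25/31 |

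The 0.20 median varies by about one patient between simulation runs, so 22-25 is a fair range for 1- to 3-month detection. P(stopped by 20) at 0.20 is 0.47-0.48 with 1- to 3-month detection and 0.17 in the 24-month case.

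P(stop) stays at 0.59 (rate 0.20) and 0.91 (rate 0.30) with 1- to 3-month detection: with 3-month detection, patient 30's outcome is known at month 30+5 = 35, just as patient 35 enrols. In the 24-month case it falls to about 0.47 and 0.79. With a maximum of 43, P(stop) is 0.55-0.59 and 0.87-0.91 across the timings from the 1-month exam to 24 months.

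**The case against.** Only the first-row result is nearly free of assumptions. Failure timing is not in the documents, the 24-month limit belongs to the primary endpoint in 20.3.1.1, and 20.2 gives its own failure definition no window. With 1- to 3-month detection the practical change is modest: P(stop) is unchanged and the 0.20 median rises by a few patients. Failures may also surface before a nominal 1-month visit, because section 11.0 has weekly physician evaluation during treatment and the exam windows are a month wide. Oversight does not rest on Table 2 alone either: section 18.0 provides DSMC meetings at least quarterly and independent DSMB review. All of this stands and limits the point. None of it rescues the 25%, which would need all five patients' failures to be visible while patient 5 is still about a month into treatment.

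Three stronger readings are tempting, and the documents do not support them.

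- **Most enrolment percentiles are too low, whatever the timing.** Seven of the 25 cells already sit at the cap of 35 and cannot rise. With 1-month detection, about 8 cells rise if the patient enrolling on the stopping day is not counted, and 13 or 14 if that patient is counted. Most cells rise only under the second convention or with later detection.
- **The rule loses most of its power to stop.** That follows only if each row is checked once, as patient n+1 enrols; P(stop) at 0.20 is then 0.05-0.48. Section 20.2 does not exclude such a check, but nothing in it prescribes one.
- **Table 1 is faulty.** The boundaries are not in question; only the description of how early they act is.

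**Conclusion.** The point holds. Table 2 and its example sentence describe a design with instant outcomes, which is not the one planned. At a true failure rate of 0.20, stopping by five patients has probability at most about 0.18 for failures visible by the end of radiotherapy, 0.04-0.10 at the 1-month exam, and about 0 at three months or later, against the stated 25%. This rests on the plan's own accrual and treatment times, on no accrual pause, and on failures not generally being evident in mid-treatment.

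Beyond that row the size depends on assumed timing. The main loss is lateness; the overall stopping probability falls materially only if failures come late. The trial remains viable, but a stated safety property is wrong and should be corrected.

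**What to change.** (a) Replace Table 2 and its example sentence with a simulation run by the sponsor. It should use one patient a month, the planned treatment and follow-up schedule, a stated range of failure timings from end of radiotherapy to 24 months, and the planned enrolment of 43 with replacement of inevaluable patients. State those assumptions beside the table, including whether a patient enrolling on the stopping day is counted. The figures above do not model inevaluable patients and should not be pasted in.

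(b) Add to 20.2 that a failure among the first n patients enrolled counts against the Table 1 row for n whenever it is identified during accrual, and that the rule is checked as soon as each failure is identified, not only at DSMC meetings. Checking only quarterly would slow it: with 1-month detection the 0.30 median rises from 10 to 12.

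Table 1 and the visit schedule are unchanged. Under (b), any trial that stops would also have stopped with no delay, so false stopping at 0.06 cannot exceed 0.046. The cost is one clarifying statement and one re-run simulation. The downside is that the restated early-stopping figures will look less favourable.
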